10.1.6.3 Pharmacokinetic Analyses

Model-derived plasma PK parameters of fenfluramine and norfenfluramine ($C_{\max_{ss}}$, $C_{\min_{ss}}$, AUC_{0-t} , AUC_{0-24}) will be summarized descriptively by treatment group when sufficient data are available. A population PK model, previously developed using data from healthy adults and pediatric patients with Dravet syndrome, will be updated to include the fenfluramine and norfenfluramine concentration-time data collected during the Maintenance Period. This model will be informed by all relevant data available at the time of data collection (both adults and pediatrics). The results from the PopPK modeling will be reported separately and conducted according to a separate SAP.

10.2 STATISTICAL ANALYSIS: PART 2

Safety and effectiveness will be assessed in the subjects who continue into Part 2 of the study in which all subjects receive open-label ZX008.

10.2.1 ANALYSIS POPULATIONS

10.2.1.1 OLE Population

Safety analyses for Part 2 will be performed on the OLE Safety Population defined as all subjects who receive at least one dose of ZX008 during the open label extension.

10.2.1.2 OLE mITT Population

The OLE mITT Population is defined as all randomized subjects who receive at least one dose of ZX008 and have valid seizure data during the open label extension.

10.2.2 TREATMENT GROUPS

All subjects in Part 2 will receive ZX008 and will be considered a single treatment group. Selected data summaries may be broken out by the treatment received during Part 1 and/or average dose received during Part 2.

10.2.3 TREATMENT PERIODS

Open-Label Extension (OLE) Treatment Period

The OLE Treatment Period covers the duration during which subjects receive open label treatment with ZX008.

OLE Taper Period

The OLE Taper Period begins immediately after the OLE Treatment period and extends for 2 weeks.

ZX008 (Fenfluramine Hydrochloride)
ZX008-1601 Clinical Study PA 4.0 (Japan) 25 July 2022

10.2.4 STATISTICAL ANALYSES AND METHODS

10.2.4.1 Safety Analyses

The number and percentage of subjects who experience treatment emergent AEs will be displayed by body system and preferred term using MedDRA. Summaries in terms of severity and relationship to study drug will also be provided. SAEs will be summarized separately in a similar manner. Laboratory tests, vital signs, physical examinations, neurological examinations, ECG, ECHO, cognition and body weight will be summarized using appropriate methods.

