2.2.1 PRIMARY OBJECTIVE

The primary objective of Part 2 is to assess the long-term safety and tolerability of ZX008 in children and adults with LGS with regard to adverse events (AEs), laboratory parameters, physical examination, neurological examination, cognition (BRIEF), vital signs (blood pressure, heart rate, temperature, and respiratory rate), ECG, ECHO, body weight, and BMI.

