Part 2 is an open-label, long-term safety study of ZX008 for subjects who have successfully completed 14 weeks of treatment (titration + maintenance) in Part 1, are candidates for continuous treatment for an extended period of time, have met the Selection Criteria for Part 1 (except for criteria related to seizure frequency), and signed informed consent/assent forms prior to the start of Part 2. Subjects who have not completed the entire 14 weeks of treatment in Part 1 may be eligible to participate in Part 2 on a case-by-case basis and only following sponsor approval. Other requirements for participation in Part 2 are described in Section 4.3. Part 2 will consist of a 12-month Open-Label Extension (OLE) Treatment Period and a 2-week Post-Dosing Period. Thus, subjects who complete 12 months of OLE in Part 2 will have been

ZX008 (Fenfluramine Hydrochloride)
ZX008-1601 Clinical Study PA 4.0 (Japan) 25 July 2022

treated with ZX008 for at least 70 weeks (including their participation in both Part 1 and Part 2). If marketing approval is not yet received after the end of the OLE Treatment Period, treatment may be extended on an annual basis in order to provide continuity of treatment for subjects who are enrolled in Part 2 of the study until ZX008 is approved in the subject's country of residence and listed on a patient's health plan formulary. Up to 5 annual extensions can be applied, for a total treatment time of 72 months in the OLE. Continuation will be based on review of safety/tolerability and effectiveness, and be offered for subjects who continue to meet eligibility requirements, comply with investigator's instructions, and for whom the investigator judges benefit outweighs risk.

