6.2.6 Clinic Visit 42: End of Study/Early Termination

The End-of-Study participation in Part 2 for an individual subject occurs after he/she has received IMP for up to 5 years in the Part 2 OLE Treatment Period, or until ZX008 is approved in a subject's country of residence and listed on a patient's health plan formulary, whichever occurs first. The End-of-Study visit may also occur if the subject withdraws participation from in Part 2 or the Sponsor terminates the study.

Subjects will visit the clinic for the End-of-Study visit if one the following events occur:

1. The subject withdraws or is withdrawn from participation in the study.
2. The Sponsor terminates the study.
3. The subject completes all study related visits and procedures (at least up to Month 12, but extensions may be granted for up to 72 months).
4. ZX008 is approved in a subject's country of residence and is listed on a patient's health plan formulary

The following procedures will be performed for subjects who did not extend Part 2 participation past 12 months:

- Review current seizure activity (number/type/duration) from diary since previous visit
- Record concomitant medications

ZX008 (Fenfluramine Hydrochloride)

ZX008-1601 Clinical Study PA 4.0 (Japan) 25 July 2022

- Complete physical examination, including height and weight, and calculation of BMI
- Complete neurological examination
- Obtain vital signs
- 12-lead ECG
- Doppler ECHO (must be performed within 3 weeks of the visit; if subject terminates early from the study, the ECHO should be scheduled as soon as practical). If the previous ECHO was completed ≤ 30 days prior to early termination, the Visit 30 ECHO will not be performed provided the parent/guardian agrees to bring the subject to the clinic for the cardiac follow-up visit (see Table 12).
- Urine or serum pregnancy test for females of child-bearing potential
- Laboratory evaluation (serum chemistry, hematology, immunoglobulin, hormones, and urinalysis) (urine for urinalysis may be collected at home, the night before the clinic visit, as long as collection procedures are followed to maintain sample stability)
- Urine or serum THC panel
- Whole blood CBD
- Collect plasma sample for AED PK evaluation (must document time of last dose)
- Tanner Staging for subjects > 7 to 18 years of age ([Appendix 5](#))
- Collect and review diary C-SSRS Since Last Visit Assessment ([Appendix 2](#))
- CGI-I (assessed by parent/caregiver)
- CGI-I (assessed by investigator)

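### For Part 2, whose primary objective is long-term safety, the only AE and SAE measure named is a crude percentage over exposure that can run from one dose to 72 months

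*Protocol*

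**What the plan says.** Section 2.2.1 sets the goal: "The primary objective of Part 2 is to assess the long-term safety and tolerability of ZX008 in children and adults with LGS", with adverse events first in the list of measures. Section 10.2.4.1 gives the AE display: "The number and percentage of subjects who experience treatment emergent AEs will be displayed by body system and preferred term using MedDRA". The synopsis (Statistical Methods, Part 2) repeats it. For serious events, "SAEs will be summarized separately in a similar manner". The rest of the safety data is treated differently: laboratory tests, vital signs, examinations, "ECG, ECHO, cognition and body weight will be summarized using appropriate methods".

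The denominator in section 10.2.1.1 is "all subjects who receive at least one dose of ZX008 during the open label extension". Section 10.2.3 defines the OLE Treatment Period as the whole time on open-label drug, without a cut-off. On its length, section 3.1 says "Up to 5 annual extensions can be applied, for a total treatment time of 72 months in the OLE". The synopsis lets participation end earlier, once the drug is approved locally and on the patient's formulary; withdrawal and early termination also end it. Section 10.2.2 pools all subjects into one group and adds: "Selected data summaries may be broken out by the treatment received during Part 1 and/or average dose received during Part 2".

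**The concern.** A percentage of subjects with an event has a clear meaning as a risk when everyone is observed for about the same time. Here the protocol builds in unequal observation. One dose is enough to enter the denominator, the end of follow-up depends partly on local approval and formulary listing, and the upper limit is 72 months. Table 2 alone provides for continuing subjects whose last visit before Amendment 4.0 falls anywhere from Month 24 to Month 36.

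For an event that keeps occurring at a steady pace, the reported percentage would then rise or fall with the mix of short and long stayers, even if the risk per year on drug never changed. A reader could not take it as a risk over a stated time, set it beside another study, or see whether events become more or less frequent with longer treatment. The protocol does normalise for time elsewhere: section 10.2.4.2 expresses drop seizure frequency per 28 days. No such step is named for AEs.

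**Working it through.** **Inputs from the protocol.** Minimum exposure: one open-label dose (10.2.1.1). Maximum: a 12-month extension plus 5 annual extensions (3.1).

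**The plan's own figure.** 12 + 5 × 12 = 72 months. Visit 42 is at OLE Day 2160, and 2160 / 30 = 72. The figure reproduces. Section 6.2.6, however, describes the end of participation for a subject who has "received IMP for up to 5 years in the Part 2 OLE Treatment Period", which is 60 months; the two statements need reconciling.

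**Assumption.** The protocol gives no Part 2 event rate and no distribution of follow-up. I assume a constant hazard h per year and show a range.

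**Step 1: crude percentage by follow-up.** Expected percentage = 1 − exp(−h × t), t in years.

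| h per year | t = 1 | t = 2 | t = 5 | t = 6 | ratio, 6 years to 1 year |
|---|---|---|---|---|---|
| 0.02 | 2.0% | 3.9% | 9.5% | 11.3% | about 5.7 |
| 0.05 | 4.9% | 9.5% | 22.1% | 25.9% | about 5.3 |
| 0.10 | 9.5% | 18.1% | 39.3% | 45.1% | about 4.7 |

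For example, at h = 0.05: 1 − exp(−0.05) = 4.9% and 1 − exp(−0.30) = 25.9%. The 5-year column shows that the 60-or-72-month question does not alter the conclusion.

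**Step 2: one pooled group with mixed follow-up.** Take h = 0.10. A share s stays 72 months and the rest leave at 6 months. The crude percentage is s × (1 − exp(−0.60)) + (1 − s) × (1 − exp(−0.05)) = s × 45.1% + (1 − s) × 4.9%.

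- s = 0.9: 41.1%
- s = 0.5: 25.0%
- s = 0.1: 8.9%

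Expected person-years to first event or exit are (1 − exp(−h × t)) / h per subject, so first events divided by person-years equals h in every case: 10.0 per 100 patient-years all three times.

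**Step 3: the order of two subgroups can reverse.** Twice the hazard (0.20) followed 12 months gives 1 − exp(−0.20) = 18.1%. The lower hazard (0.10) followed 72 months gives 45.1%. The lower-risk subgroup looks worse.

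**The case against.** The strongest reply is that this belongs in the SAP. Section 10.1.6 defers the full methods there, nothing in 10.2.4.1 calls the percentage the only or main summary, and exposure-adjusted rates are often added in table shells. It is fair that the text does not exclude them. But measure, denominator and period are all stated, and an analysis that reported crude percentages alone would comply in full. The point concerns a measure stated in the protocol that is poor for its own objective.

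Number and percentage is also a legitimate description of cumulative occurrence in an uncontrolled extension. That stands, and it is a reason to keep the display and add to it.

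Four stronger inferences are tempting and are not supported:

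- That the whole Part 2 safety result is fixed as crude percentages. Only AEs and SAEs have a named format; ECHO, ECG, laboratory and weight analyses are left open.
- That late valve findings or pulmonary hypertension could not be followed over time. Scheduled, centrally read ECHOs permit summaries by visit, whatever the AE table shows.
- That a split by average dose will create a false dose trend. The split is optional and AE tables are not named. The direction is uncertain: all subjects start at the same low dose, so very early leavers have low averages and short follow-up. But section 5.5.6 allows decreases for tolerability and earlier increases for worsening seizures, and subjects who do well may stay long on the starting dose.
- That follow-up drives the percentages as much as risk does. That needs event rates and a follow-up distribution the protocol does not give. Events clustered early, or experienced by nearly everyone, depend on it less; in the earlier open-label study (section 1.3), 317 of 330 subjects had at least one TEAE.

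Finally, Part 2 has a single treatment group, so no randomised comparison is biased.

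The interim analysis after all Cohort B subjects complete 12 months (section 10.1) does not settle the matter, because no data cut at Month 12 is stated and earlier entrants would contribute more time.

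**Conclusion.** The concern holds for AEs and SAEs in Part 2. The protocol names one measure, the crude percentage, under follow-up that it allows to vary from one dose to 72 months. For events that accrue over time, that measure mixes risk with length of observation. The size, between 1 and 6 years of follow-up, is roughly a five-fold change in the percentage at unchanged risk, for hazards of 2 to 10% per year. This rests on the assumed constant hazard and illustrative follow-up times; the actual distortion depends on rates and a spread of exposure that are not in the document, and it is smaller for early events. The change is worth making because it bears on the primary objective of Part 2 and a better measure is available from data already collected. It does not extend to the other safety data.

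**What to change.** In section 10.2.4.1 and the matching synopsis text:

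1. Keep number and percentage of subjects, and give them also for a common first-12-month window. Subjects who leave before Month 12 still contribute less time, so state how many do.
2. For the whole extension, add exposure-adjusted incidence of AEs and SAEs: subjects with a first event per 100 patient-years, counted from the first open-label dose to first event or end of observation, with 95% CI.
3. Because a single rate averages over time, add cumulative incidence by year for late-onset events of interest, with the number still at risk.
4. If AE summaries are broken out by dose, use dose at onset with person-time on that dose, since average dose can be confounded with length of follow-up.

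Separately, reconcile the maximum duration of Part 2 between sections 3.1 and 6.2.6.

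The cost is some wording and a few extra tables. AEs and dosing are already recorded, so no new data collection is needed.

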10.2.4.2 Effectiveness Analyses

Effectiveness will be assessed by the change from baseline (prior to randomization into Part 1) in DSF. The DSF per 28 days will be calculated as the number of seizures recorded divided by the number of days in the period and multiplied by 28. The change in DSF during the OLE Treatment Period will be calculated as the difference between DSF during the OLE and the baseline DSF measured prior to randomization in Part 1. The percent change in DSF is the change in DSF between OLE and Baseline / DSF during Baseline x 100. Both the mean and median percent change in DSF will be presented and the statistical significance of the percent change will be assessed using a Wilcoxon signed-rank test. Other secondary assessments will be compared to baseline from prior to Part 1, or by visit throughout Part 1 and Part 2, as appropriate.

For subjects continuing in Part 2 past Visit 22, effectiveness will be assessed by investigator rating of overall change in seizure frequency (<25%, ≥25%, ≥50%, or ≥75%, 100% (seizure-free) improvement compared to last visit).

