The primary objective of Part 2 is to assess the long-term safety and tolerability of ZX008 in children and adults with LGS with regard to AEs, laboratory parameters, physical examination, neurological examination, vital signs, ECG, ECHO, body weight, and BMI.

The number and percentage of subjects who experience treatment emergent AEs will be displayed by body system and preferred term using MedDRA. Summaries in terms of severity and relationship to study drug will also be provided. SAEs will be summarized separately in a similar manner. Laboratory tests, vital signs, physical examinations, neurological examinations, ECG, ECHO, cognition and body weight will be summarized using appropriate methods.

Effectiveness will be assessed by the change from baseline (prior to randomization into Part 1) in DSF. The DSF per 28 days will be calculated as the number of seizures that result in drops divided by the number of days in the period and multiplied by 28. The change in DSF during the first 12 months of

ZX008 (Fenfluramine Hydrochloride)

ZX008-1601 Clinical Study PA 4.0 (Japan) 25 July 2022

Part 2 OLE Treatment Period will be calculated as the difference between DSF during the OLE and the baseline DSF measured prior to randomization in Part 1. Both the mean and median percent change in DCF will be presented and the statistical significance of the percent change will be assessed using a Wilcoxon signed-rank test. Other secondary assessments will be compared to baseline from prior to Part 1, or by visit throughout Part 1 and the first 12 months of Part 2, as appropriate.

PUBLIC COPY
This document cannot be used to support any marketing authorization application and any extensions or variations thereof.

ZX008 (Fenfluramine Hydrochloride)
ZX008-1601 Clinical Study PA 4.0 (Japan) 25 July 2022

Table 1. Schedule of Assessments: Part 1

| Study Assessments – PART 1 | Baseline Period ^a | | | Titration + Maintenance Period | | | | | | | | EOS/ ET ^b | Post- Dosing ^l | Cardiac Follow- up ^c |
|--|------------------------------|--------------|-------------------------|--------------------------------|-----------------|----------------|--------------------|----------------|--------------|----------------|---------------|-------------------------|------------------------------|---------------------------------------|
| | Screening | 2 (Phone) | Random- ization 3 | Titration Period | | | Maintenance Period | | | | | | | |

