7.1.1 Seizure Assessments

Seizure frequency by type and duration will be recorded daily by the parent/caregiver in a diary during Part 1 and up to 12 months in Part 2 (i.e., up to Visit 22). Seizure types include:

- A: Hemiclonic (note lateralization – right body, left body, or independent right and left)
- B: Focal With or Without Retained Awareness
- C: Secondly Generalized Tonic Clonic (evolving to bilateral convulsive seizure from focal seizure)
- D: Generalized Tonic Clonic Convulsion
- E: Absence or Atypical Absence
- F: Myoclonic
- G: Tonic
- H: Atonic
- I: Clonic
- J: Tonic/Atonic (cannot differentiate)
- K: Infantile Spasms (if under 3 years of age)
- L: Epileptic Spasms (if 3 years of age and older)
- O: Other*

* “Other” indicates a seizure type that cannot be classified in any of the above seizure

ZX008 (Fenfluramine Hydrochloride)
ZX008-1601 Clinical Study PA 4.0 (Japan) 25 July 2022

types A-L. All other seizures must be classified appropriately based on the Investigator's medical opinion and Epilepsy Study Consortium approval.

Parents/caregivers will also indicate in the diary entry whether the seizure resulted in a drop, or would have resulted in a drop were it not for the position (ie, in a chair). This includes seizures involving the entire body, trunk, or head that led to a fall, injury, slumping in a chair, or the subject's head hitting a surface or that could have led to a fall or injury, depending on the patient's position at the time of the seizure.

Efficacy/effectiveness endpoints that will be derived from the diary data include frequency of seizures that result in drops and seizures that do not result in drops, motor seizures, and all seizures, and the number/duration of seizure-free intervals.

Seizures that evolve into status epilepticus (SE) will be captured by type and duration (>10 minutes) as are all seizures. SE should be entered as an SAE if a prolonged seizure or series of seizures persists for 30 minutes or longer, regardless of administration of rescue medication, *and* is either diagnosed by a medical professional or occurs more than once in a day. SE lasting for less than 30 minutes should be entered as an AE, unless one of the other SAE criteria (eg, hospitalization) are met. If this incident involves multiple seizures close in time, the SE definition applies if the seizures are close together such that consciousness is not regained between ictal events.

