After 12 months in Part 2, seizure diaries are not required. Rather, based on discussions with the parent/caregiver, clinical evaluation, and review of any documentation provided by the caregivers, investigators will assess the percent improvement in seizure burden on a 5-point scale: <25%, ≥25%, ≥50%, ≥75%, 100% [ie, seizure-free] improvement.

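### Read literally, Sections 10.2.3 and 10.2.4.2 divide a 12-month diary count by up to 72 months of days, and contradict the synopsis on both period and numerator

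*Protocol*

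**What the plan says.** The Part 2 rule has to be put together from several places in the protocol.

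- **Formula.** Section 10.2.4.2 says DSF per 28 days is "calculated as the number of seizures recorded divided by the number of days in the period and multiplied by 28".
- **Period it applies to.** The same section continues: "The change in DSF during the OLE Treatment Period will be calculated as the difference between DSF during the OLE and the baseline DSF". It states no 12-month limit.
- **Definition of that period.** Section 10.2.3: "The OLE Treatment Period covers the duration during which subjects receive open label treatment with ZX008".
- **Length of open-label treatment.** Section 3.1: "Up to 5 annual extensions can be applied, for a total treatment time of 72 months in the OLE".
- **Diary collection.** Section 7.1.1 runs the diary to Visit 22 and then says: "After 12 months in Part 2, seizure diaries are not required".
- **Synopsis, Statistical Methods, Part 2.** DSF is "calculated as the number of seizures that result in drops divided by the number of days in the period", times 28, and the change in DSF is taken over the first 12 months of the OLE Treatment Period only.

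The period name has two meanings. The synopsis (Methodology) and Section 3.1 describe a 12-month OLE Treatment Period with annual extensions after it ends. Section 6.2.6 speaks of a subject who has "received IMP for up to 5 years in the Part 2 OLE Treatment Period", and Table 2 places every visit from 15 to 42 under the heading OLE Treatment Period.

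**The concern.** A rate is only meaningful if events are counted over the same time as the denominator. On the definitions in Section 10.2, counting stops at Month 12 but days keep accruing for as long as the subject is treated. The computed rate then falls with time on treatment, whatever happens to the seizures.

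The numerator raises a separate problem. The diary in Section 7.1.1 records all seizure types, with a flag for drops. Baseline DSF counts drops only (Sections 7.1 and 10.1.5). Counting all recorded seizures in Part 2 would compare two different quantities and push the result upward.

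At stake is the first-listed effectiveness measure of Part 2. Its percent change is tested with a Wilcoxon signed-rank test, and the proportion with at least a 50% reduction is also a Part 2 endpoint (Section 2.3.1). The case is a practical one. A final analysis is planned when the last Cohort B subject completes Part 2, and Table 2 provides for subjects already at Months 24 to 36 when this amendment is approved.

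**Working it through.** The protocol gives no numerical result for Part 2 DSF, so there is no figure to reproduce. The check applies the stated formula to a subject whose seizures do not change.

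**Inputs**
- Diary period: 360 days (Visit 22 is OLE Day 360 in Table 2), assumed complete.
- Literal denominator: D days of open-label treatment, up to 2160 (Visit 42 in Table 2, Month 72).
- Baseline DSF: b per 28 days. Its value cancels.

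**Formula**
- Seizures recorded = b × 360/28.
- DSF = (b × 360/28) / D × 28 = b × 360/D.
- Percent change = (360/D − 1) × 100.

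| Open-label months | D (days) | Percent change, no true change |
|---|---|---|
| 12 | 360 | 0.0% |
| 24 | 720 | -50.0% |
| 36 | 1080 | -66.7% |
| 48 | 1440 | -75.0% |
| 60 | 1800 | -80.0% |
| 72 | 2160 | -83.3% |

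As an illustration, take b = 20. Then 20 × 360/28 = 257.1 seizures are recorded. Over 2160 days that is 257.1/2160 × 28 = 3.33 per 28 days, and (3.33 − 20)/20 = -83.3%.

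For a true proportional change d, the result is (1 + d) × 360/D − 1. A subject whose seizures doubled (d = 1) would show 2 × 360/2160 − 1 = -66.7% at 72 months. An unchanged subject would meet the 50% reduction threshold from Month 24.

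**With the synopsis limit.** D = 360, so the unchanged subject shows 360/360 − 1 = 0.0%.

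**Numerator.** Let s be the share of a subject's recorded seizures that are drops. Over the 12 diary months, an all-seizure numerator against a drop-only baseline gives 1/s − 1 for an unchanged subject, which is zero or positive. The protocol gives no value for s, so this cannot be sized. It works against the denominator effect.

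**The case against.** The strongest reply is that the protocol as a whole points to 12 months. The synopsis says so for this very analysis. The synopsis and Section 3.1 call the OLE Treatment Period 12 months, and extensions are repeatedly described as following its end. Section 10.2.4.2 itself closes by assessing subjects beyond Visit 22 with an investigator rating. On the numerator, Section 10.1.6.1 defines DSF as a drop-seizure frequency, so the wording in Section 10.2.4.2 looks like a drafting slip.

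Much of this stands. A reader might infer from Section 10.2 that the analysis will divide 12 months of counts by up to 72 months of days. The documents do not support that as the intended calculation, because several passages point the other way. It would also be wrong to say that the synopsis alone supplies the 12-month limit.

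The contradiction remains all the same. Section 10.2.3 is the definition written for the Part 2 analysis, and it takes the long meaning; Section 6.2.6 and Table 2 also use the term beyond 12 months. The synopsis states the 12-month limit twice, for the DSF change and for the other secondary assessments, and Section 10.2.4.2 omits it both times. The investigator rating adds a later measure but does not shorten the DSF denominator.

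A reader might also infer that days without a diary entry are counted as seizure-free. Section 10.2.4.2 does not say how such days are treated, and that detail is commonly left to the SAP. Nor is any error shown for baseline or for the titration plus maintenance period: Section 10.1.6.1 uses all available data without imputation.

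**Conclusion.** The point holds as an internal contradiction in the protocol. On its own definitions, Section 10.2 gives the wrong answer for Part 2 DSF. It also conflicts with the synopsis on the denominator period and on which seizures are counted. For the same unchanged subject, one part of the protocol gives 0% and another gives -50% at 24 months, -67% at 36 and -83% at 72. Those figures rest on the literal reading of Sections 10.2.3 and 10.2.4.2 and on a complete diary for 360 days.

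A reader might go further and conclude that the long-term effectiveness result is uninterpretable. The documents do not support that, because applying the synopsis limit removes the denominator artefact. Part 2 is primarily a safety study (Section 2.2.1). DSF change there is a secondary, single-arm, open-label measure (Section 2.2.2) outside the Part 1 testing hierarchy, and the Part 1 primary analysis is unaffected. This is a moderate correction, not one on which the trial's main conclusion depends.

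**What to change.** - In Section 10.2.4.2, define Part 2 DSF as 28 × (number of drop seizures) / (number of days with diary data), from OLE Day 1 to Visit 22 (Month 12) or earlier discontinuation.
- Use OLE Treatment Period in one sense in Sections 3.1, 6.2.6 and 10.2.3 and in Table 2, with a separate name for the annual extensions.
- Carry the synopsis's 12-month limit into both sentences of Section 10.2.4.2 that lack it, and make the synopsis formula match the new definition.

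Using days with diary data also prevents unrecorded days from being counted as seizure-free. How much that matters depends on diary completeness, which the protocol does not give.

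The cost is a few sentences of protocol wording, the same wording in any SAP, and one programming rule. It should be settled before the final Cohort B analysis. No data collection changes.
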